### 7.3 Multiplicity

The study is to be conducted with PFS and OS as 2 primary endpoints with the goal of a regulatory approval based on either PFS or OS. The overall type I error probability is specified to be 1-sided 0.025 with success for either of the 2 primary endpoints defining study success using the Bonferroni method to specify that each endpoint will be evaluated using a type I error probability of 1-sided 0.0125 in order to protect the overall type I error. In case both final PFS analysis and final OS analysis have 1-sided  $0.0125 \leq p < 0.025$ , or one of the analyses has 1-sided  $0.0125 \leq p < 0.025$  while the other has 1-sided  $p < 0.0125$ , the overall type I error will be controlled at 1-sided 0.025 with statistical significance applied to both PFS and OS analyses using the Hochberg method.

### 7.4 Interim Analyses and Data Monitoring

A data monitoring committee will be established with the responsibility of safeguarding the interest of study subjects and maintaining the overall integrity of the study. The DMC will review safety data periodically during the study as described under Section 8.17 (Data Monitoring Committee) of the protocol and will evaluate the results of final PFS analysis and a planned interim OS analysis to assess futility with the possibility of a recommendation for stopping the study early because of futility. The OS non-binding futility boundary is set to be HR = 1.0. It will be conducted at 67% of information time (120th death event from the 179 required death events for final OS analysis). If deemed necessary by the DMC, unblinded data may be reviewed on a case-by-case basis. The sponsor will remain blinded to study treatment until either

1 of the 2 primary endpoints is met or until the study has been stopped early. Details of DMC function will be governed by a DMC Charter developed by the sponsor and accepted by DMC members.

## **8 STATISTICAL ANALYSIS**

### **8.1 Study Population**

#### **8.1.1 Subject Disposition**

Subject disposition and the incidence of study discontinuation (and reason for discontinuation) will be tabulated for all enrolled patients by treatment arm. The information will be summarized as follows for subject disposition per treatment arm and overall:

- Subject Status (Prime Phase [Day 1 to 92], Boost Phase [Day 92 up to Day 365], Post Treatment Period [Last dose to PD], and Long Term Follow-up [PD to end of study])
- Treatment Completed
- Primary Reason for Treatment Discontinuation (as reported on CRF)
- Study Completed
- Primary Reason for Study Discontinuation (as reported on CRF)

At the same time, the number and percentage of subjects in each analysis set and reason for excluding from the specified analysis set will also be tabulated.

Listings will be presented for data relevant to subject disposition.

#### **8.1.2 Protocol Deviations**

The clinical study team will define CSR reportable protocol deviation and major protocol deviation to be excluded from efficacy evaluable set. They clinical team will have quarterly review of all potential CSR reportable and major protocol deviations during study conduct and prior to database lock. CSR reportable and major protocol deviations will be categorized by deviation type. The subject incidence of CSR reportable protocol deviation (IPD) will be summarized by deviation type based on safety set.

A listing will be provided for all protocol deviations.

#### **8.1.3 Demographic and Baseline Characteristics**

All demographics and baseline characteristic variables will be summarized by treatment arm and overall for ITT set.

- Demographic and baseline characteristics data, including age (continuous and grouped as <65, or ≥65 years), sex, childbearing potential, race, ethnicity, weight, height, BMI and ECOG will be summarized.
- Disease history and characteristics will be summarized and include:
  - Time from Initial Diagnosis (month) [(date of randomization – date of initial diagnosis + 1)/30.4375]
  - TNM separated stage at initial diagnosis
  - AJCC stage at initial diagnosis
  - Grade (French or FNCLCC) at initial diagnosis
  - t(X;18) Translocation
  - BCOR 6 Present
  - Tumor Monophasic or Biphasic
  - Any Prior Cancer Related Treatment (Yes, No)
  - Any Prior Cancer Related Surgery (Yes, No)
  - Type of prior therapy (adjuvant/neoadjuvant chemotherapy and surgery and/or radiotherapy)
  - First-Line systemic anti-cancer therapy (regimen, number of cycles, type, best response, total dose)

## 8.2 Efficacy Analyses

The efficacy analysis will be performed based on ITT set and supportive analysis will be performed based on EE set.

For PFS and ORR, primary analyses will be performed for the scan results determined by the investigator assessment, scan results by independent radiological review (IRC), if required, will be the supportive analysis.

### 8.2.1 Analytic Standard

#### 8.2.1.1 Data Cutoff Date

Associated with each analysis is a data cutoff date. The key analyses will use the data cutoff date to censor event dates, and this may result in an event date turning into a censored date. Additional sensitivity analyses without data cutoff censoring will also be done when there has been data cutoff censoring, especially when data cutoff censoring results in loss of events.

### **8.2.1.2 Assessing Clinical Site Homogeneity**

It is important to assess clinical site homogeneity with respect to the primary and secondary outcomes. Following is the method that will be used to obtain a descriptive assessment of clinical site homogeneity.

Assume each clinical site is identified by a unique code. It is often the case that one or more clinical sites will fail to have at least one subject assigned to each arm. All such clinical sites are to be pooled into a new pseudo clinical site with a new unique code. This new pseudo clinical site is to be used in the following analyses. A forest graph with sites or a grouping of sites will be created where the effect estimate will be displayed along with the 95% confidence interval. This graph is most effectively displayed if the estimates are sorted by estimate size.

## **8.2.2 Analysis of Primary Efficacy Variables**

### **8.2.2.1 Primary Analyses**

The null hypothesis of no difference in PFS/OS between CMB305 and placebo, in the ITT set, will be tested using a stratified log-rank test stratified by randomized stratification factors: disease status at screening (locally advanced unresectable versus metastatic), tumor response during screening (PR/SD versus CR/NED), and by baseline presence of anti-NY-ESO-1 antibody (yes versus no)).

The null hypothesis will be rejected and it will be concluded that PFS/OS on CMB305 is superior to that on placebo if the 1-sided p value at the final analysis for the stratified log-rank test is less than the pre-specified alpha as discussed in Multiplicity Section. Success for either of the 2 primary endpoints defines study success.

The Kaplan-Meier curve will summarize PFS/OS graphically by treatment arm. Tabular summaries of the Kaplan-Meier curves, including the median and 2-side 97.5% and 95% CI will be provided by treatment arm. The 4, 6, 8, and 10 month PFS rate and 12, 18, 24, and 30 month OS rate will be provided by treatment arm.

The associated HR and its 2-sided 97.5% and 95% CI will be provided using the stratified Cox proportional hazard model for PFS/OS, comparing treatment arm, stratified by the randomized stratification factors .

The final PFS analysis will be conducted when a total of 141 PFS events occur. The final OS analysis will be conducted when a total of 179 deaths occur.

### **8.2.2.2 Sensitive Analysis of Primary Endpoints (PFS/OS)**

The sensitive analyses of primary endpoints will include:

- OS using the Safety set, according to the treated arm

- PFS by investigator assessment and OS using the EE set
- PFS by investigator assessment in the ITT set, with start of subsequent anti-cancer therapy as a PFS event
- PFS based on the IRC response assessment, if required, for both ITT and EE sets as supportive analysis
- Stratified Cox proportional hazard model for PFS or OS, in ITT set, with additional covariates of number of cycles in first line chemotherapy, and/or type of prior therapy (adjuvant/neoadjuvant chemotherapy and surgery and/or radiotherapy)
- PFS and OS by Fleming-Harrington weighted log-rank test with  $\rho = 0$ ,  $\gamma = 1$ , for adjustment of delayed effects.
- The Fleming-Harrington weight for late effects is defined as below
 
$$W_n(t) = (S_n(t))^{\rho} (1 - S_n(t))^{\gamma}$$
- PFS and OS by piecewise Cox proportional model in presence of non-proportional hazard for time-varying treatment effect:
 
$$h(t | z_i) = h_o(t) \exp(\alpha z_{1i} + \beta_1 z_{2i} 1(t \leq c_i) + \beta_2 z_{2i} 1(c_i < t \leq c_{i+1}) + \beta_3 z_{2i} 1(t > c_{i+1}))$$

Where  $Z_{1i}$  is time-independent covariates such as stratification factors;  $C_i$  and  $C_{i+1}$  are cut points (e.g. 4 and 8 months, respectively) for time period and  $I(\cdot)$  denotes the indicator function.
- PFS and OS not censoring events that occur after the cutoff.
- OS with competing events being taken into consideration. Competing events for death are “definite” lost to follow-up and withdrawal of consent for continued survival assessments. Both of these competing events are subject to revision for an individual subject with the passage of time. The cumulative incidence estimates will be plotted if the percent of subjects with competing events in either arm exceeds 3%.
- PFS with competing events being taken into consideration. Competing events for PFS event are lost to follow-up, withdrawal of consent, start of other anti-cancer therapy, or two or more missing scans prior to a PFS event. The cumulative incidence estimates will be plotted if the percent of subjects with competing events in either arm exceeds 3%.

### 8.2.2.3 Other Analyses of Primary Endpoints (PFS/OS)

- Strata homogeneity will be assessed by including arm by stratum interaction with main effect terms in the Cox proportional hazard model. If the 2-sided p value for this test of

homogeneity is significant at two-sided 0.10, then the stratum-specific hazard ratio estimates and confidence intervals will be computed. If the statistical criterion is not met then the test of homogeneity will be regarded as an exploratory analysis of the data collected. Thus, the outcome of the strata homogeneity test will not affect the interpretation of significance for the primary test, but will affect the way the results are presented or subsequently analyzed.

- Clinical site homogeneity will be assessed by including in the model site grouping multi-level main effect terms and also interaction terms for arm by categorical site grouping.
- Effect modifier analyses will be performed for putatively prognostic factors, including those explored previously in the literature as well as those hypothesized to be predictive in the context of this study. Effect modification will be assessed one factor at a time in stratified models. Each factor will be analyzed as either a natural dichotomy, a dichotomized ordered categorical with cut point chosen based on biologic considerations, or a continuous variable dichotomized at the overall median. A separate effect size estimate for arm and its 95% confidence interval will be computed for each level of the dichotomy using SAS. The four Kaplan-Meier estimates (arm by factor) for each of the factors analyzed as effect modifiers will be plotted on one graph.
- Cox proportional hazard models with multiple added prognostic covariates will be estimated. The covariates to be added will include those explored previously in the literature as well as those hypothesized to be predictive in the context of this study. Variable selection method such as stepwise method will be used to build the multivariate Cox proportional hazard model. Interactions will also be explored for contribution to the model.

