1.1.2 Overview of Data Generated from Initial Clinical Development of CMB305

Individual components of the CMB305 regimen, LV305 and G305, were first evaluated in separate phase 1 studies, followed by a phase 1 study of the CMB305 regimen:

- **ID-LV305-2013-001** is a phase 1, open-label study designed to evaluate the safety, tolerability, and immunogenicity of intradermally (ID) administered LV305 in subjects with locally-advanced, relapsed, or metastatic cancer expressing NY-ESO-1
- **G305/IDC-G305-2013-001** is a phase 1, open-label, multiple ascending dose study evaluating the safety, tolerability, and immunogenicity of the intramuscular (IM) NY-ESO-1 protein with GLA-SE adjuvant in subjects with unresectable or metastatic cancer expressing NY-ESO-1
- **IMDZ-C131** is a phase 1, open-label study designed to evaluate the safety, tolerability, and immunogenicity of ID or subcutaneously (SC) administered CMB305 in subjects with locally-advanced, relapsed, or metastatic cancer expressing NY-ESO-1

Based on the mechanism of action, rapid tumor shrinkage is not expected from CMB305 therapy, and clinical benefit should be assessed beyond disease progression as determined by conventional RECIST. Thus, CMB305 clinical development is focused on understanding long-term benefit including overall survival (OS) in the early clinical studies.

While subjects with different NY-ESO-1+ solid tumors including several types of soft tissue sarcoma (STS) have been enrolled in the LV305-2013-001 and IMDZ-C131 clinical studies, subjects with synovial sarcoma emerged as the primary focus of clinical development due to the uniformly high expression level of NY-ESO-1 in these tumors. Thirty-four NY-ESO-1+ subjects with synovial sarcoma were treated on studies LV305-2013-001 and IMDZ-C131. The vast majority of subjects with synovial sarcoma in both studies received prior systemic chemotherapy, had metastatic disease, and a high level of NY-ESO-1 expression by immunohistochemistry (IHC) (Somaiah 2017a; Somaiah 2017b), which is associated with a worse prognosis (Nicholaou 2006; Jungbluth 2001a; Van Tine 2016; Komarov 2017).

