## 4 SAMPLE SIZE DETERMINATION

A total of 248 subjects will be randomly assigned in a 1:1 ratio such that 124 subjects will be included in each of the 2 treatment arms. The study is powered at 90% with 179 death events required to detect a HR of 0.59, which corresponds to a 41% reduction in the risk of death, and an approximately 69% increase in median survival compared with a placebo median survival of 20 months, and uses a 1-sided log-rank test, with an alpha of 0.0125, a 1:1 randomization ratio, and an interim OS non-binding futility analysis with boundary of HR = 1.0 at 67% of information time (120 death events from the 179 required death events for the final OS analysis). A total of 248 subjects will yield the 179 events required, under the assumption of 24 months for enrollment (25% of subjects enrolled in the first year and 75% of subjects enrolled in the second year) plus 42 additional months of follow-up.

With 141 PFS events, the study is powered at 90% to detect a HR of 0.55, which corresponds to a 45% reduction in the risk of PFS events (either disease progression or death), and an approximately 82% increase in median PFS compared with a placebo median PFS of 4 months, and uses a 1-sided log-rank test, with an alpha of 0.0125, and a 1:1 randomization ratio.

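### The effect-modifier analysis of PFS and OS takes continuous factors only as a median split and never estimates the interaction; a continuous arm-by-factor term is a cheap, minor improvement

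*SAP*

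**What the plan says.** The effect-modifier bullet of SAP 8.2.2.3 covers prognostic factors from the literature and factors thought likely to predict benefit in this trial. It names none of them. The method is: "Effect modification will be assessed one factor at a time in stratified models". A factor that is not already binary is handled as "a dichotomized ordered categorical with cut point chosen based on biologic considerations, or a continuous variable dichotomized at the overall median". So ordered categories get a biologically chosen cut, and continuous variables get the sample median. The bullet offers no continuous option.

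The planned output is: "A separate effect size estimate for arm and its 95% confidence interval will be computed for each level of the dichotomy using SAS", plus a Kaplan-Meier plot with four curves (arm by factor level). The bullet states no interaction test, significance level, target interaction or power.

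Two neighbouring bullets matter. The first tests an arm-by-stratum interaction and gives stratum-specific hazard ratios if "homogeneity is significant at two-sided 0.10". The last describes multivariable Cox models built by stepwise or similar selection and adds: "Interactions will also be explored for contribution to the model". It does not say how continuous covariates are coded.

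**The concern.** Splitting a continuous factor at its median treats everyone in a half as alike. If the benefit of CMB305 changes gradually with the factor, much of the evidence for that gradient is lost. The two subgroup hazard ratios also depend on where the median of this sample happens to fall. Two separate confidence intervals do not answer the question asked either: whether the effect differs needs an estimate of the difference, and this bullet does not call for one.

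Percent NY-ESO-1 expression is a possible example, though the SAP does not name it. Eligibility starts at 1% expression. Protocol 1.1.2 explains the choice of synovial sarcoma as "due to the uniformly high expression level of NY-ESO-1 in these tumors". If that holds in the trial, a median cut would separate high expressers from slightly higher ones and pool the few low expressers with the rest of the lower half.

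At stake is what can be learned about who benefits from a trial of 248 subjects in a very rare disease. The primary conclusions are not at stake.

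**Working it through.** **Inputs from SAP section 4.** "The study is powered at 90% with 179 death events required to detect a HR of 0.59". "With 141 PFS events, the study is powered at 90% to detect a HR of 0.55". One-sided alpha is 0.0125 per endpoint, allocation 1:1, N = 248. Placebo medians are 20 months (OS) and 4 months (PFS). Accrual takes 24 months, with 25% enrolled in the first year and 75% in the second.

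**Step 1: reproduce the plan's own figures.** Schoenfeld: D = 4(z₀.₉₈₇₅ + z₀.₉₀)² / (ln HR)², with (2.241 + 1.282)² = 12.41.
- OS: 4 × 12.41 / (ln 0.59)² = 49.6 / 0.2784 = 178.3, so 179 deaths, as stated. Power is 90.1%, and still 90.1% with the futility look at 120 deaths.
- PFS: 49.6 / (ln 0.55)² = 49.6 / 0.3574 = 138.9, so 139 events against 141 stated. Power at 141 events is 90.5%.

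Both agree with the plan. Neither says anything about power for effect modification.

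**Step 2: information kept by a median split.** When the interaction is linear in the factor, the split keeps the squared correlation between the factor and its own split.
- Normal factor: 2/π = 0.637, so 36% is lost. For the interaction, 141 PFS events then carry what 141 × 0.637 ≈ 90 would carry with the factor kept continuous, and 179 deaths what 179 × 0.637 ≈ 114 would.
- Uniform: 75% kept. Exponential: 48% kept. Skewed towards high values, Beta(4,1): 61% kept.

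**Step 3: illustrative power, normal factor, two-sided 0.05.** With 1:1 allocation, the expected z for the arm-by-factor term is (√D / 2) × ln(R), where R is the ratio of hazard ratios per SD of the factor. The split multiplies this by √(2/π) = 0.798.

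Worked case, OS, R = 1.4: (√179 / 2) × 0.3365 = 6.690 × 0.3365 = 2.25, so power is Φ(2.25 − 1.96) = 61%. After the split, 2.25 × 0.798 = 1.80, so power is Φ(1.80 − 1.96) = 44%.

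| R per SD | PFS: continuous / split (%) | Loss | OS: continuous / split (%) | Loss |
|---|---|---|---|---|
| 1.2 | 19 / 14 | 5 | 23 / 16 | 7 |
| 1.4 | 52 / 36 | 16 | 61 / 44 | 18 |
| 1.5 | 67 / 48 | 19 | 77 / 58 | 19 |
| 1.6 | 80 / 61 | 19 | 88 / 71 | 17 |
| 1.8 | 94 / 80 | 14 | 98 / 88 | 10 |
| 2.0 | 98 / 91 | 8 | 99.6 / 96 | 4 |

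Losses are in percentage points, computed before rounding. The maximum is about 19. At a two-sided level of 0.10 it is about 17.

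**Step 4: simulation check.** Cox models without strata, 1,500 trials per setting, with the SAP's sample size, medians, hazard ratios, accrual and event counts. For R from 1.2 to 1.8 the loss was about 5 to 22 points for PFS and about 5 to 20 for OS. Monte Carlo error is about 1.3 points per power figure.

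**Step 5: change the assumptions.**
- Uniform factor: loss of at most about 12 points.
- Exponential factor: up to about 31 points.
- Effect that steps exactly at the median: the split beats the linear term by about 7 to 20 points. For OS with a ratio of 2.0 between halves, power is 64% with the split and 46% with the linear term.

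**The case against.** The strongest reply is that the bullet plans estimates and plots, not a test, so a power loss measures something the SAP never promised. That stands as a limit on the power figures. It does not remove the information loss, which affects the precision of any estimated gradient just as it affects a test.

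A second reply is that the last bullet of the section leaves room for continuous interactions. It does leave room, but it prespecifies no interaction and no coding, and it relies on data-driven selection. It does not replace a prespecified arm-by-factor analysis.

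Third, a median fixed in advance is blind to arm and outcome and so prevents a search for a favourable cut. That is a real merit and a reason to keep the split as a display. The biologically chosen cuts for ordered categories are likewise reasonable.

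Fourth, the obvious examples are weaker than they look. Baseline antibody is already a yes/no stratification factor, and Protocol Table 3 gives a titer threshold of 1:100. SAP 5.1.3 sends the immune and tissue biomarker work to a supplemental SAP that is not available here. If expression really is uniformly high, a continuous term has little spread to work with as well, and stating the interaction per SD hides this.

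Last, the moderate interactions that give the largest losses are not small. At R = 1.5 around an OS hazard ratio of 0.59, the hazard ratio runs from 0.59 / 1.5 = 0.39 to 0.59 × 1.5 = 0.89 between one SD on either side of the mean.

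**Conclusion.** The point holds as a minor one. For continuous factors the effect-modifier bullet prespecifies only a median split and gives no estimate of the difference between halves. For a roughly normal factor with a log-linear interaction, about 36% of the information on that interaction is discarded. Over interaction ratios of 1.2 to 1.8 per SD, that is about 5 to 20 points of power in a two-sided 0.05 test, and about 15 to 20 for moderate interactions.

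A reader might infer a fixed cost of around 20 points in finding out who benefits. The documents do not support that. They give no factor, distribution, interaction size, shape, test level or power target for this analysis. Under other assumptions the result runs from a gain for the split to a loss of about 30 points.

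A reader might also infer that the trial's main conclusions are weakened. They are not. The primary tests are log-rank tests stratified by three binary factors, and neither they nor the type I error control or the gated secondary tests use these splits.

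**What to change.** Add to the effect-modifier bullet of SAP 8.2.2.3, before database lock:

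*Continuous factors will also be analysed on their measured scale (log scale for titers). Effect modification will be estimated by the arm-by-factor interaction in the stratified Cox model, using a linear term with a restricted cubic spline as a check. The estimated hazard ratio and its 95% CI will be plotted across the range of the factor. These analyses are exploratory.*

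Keep the median split for the Kaplan-Meier display and the subgroup estimates, and leave ordered categories with biologically chosen cut points as they are. The section already uses an interaction term for the strata, so the approach is not new to this plan.

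The cost is SAP wording, a few lines of code and slightly more output. No extra data are needed and alpha is untouched. The drawback is reliance on a linear form, which the spline checks. The exploratory label matters because several unnamed factors may be examined without a multiplicity rule.
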